7.2.5. Clinical Laboratory Tests

Required clinical laboratory tests are listed in Section 9.2. Specific instructions for collection, processing, storage, and shipment of clinical laboratory samples will be provided in separate laboratory manual(s).

It is not required for laboratory samples to be collected under fasted conditions. The date and time of the sample collection must be documented on the laboratory report. Investigators must review and sign laboratory reports and document the clinical significance of each laboratory abnormality. New clinically significant laboratory abnormalities or clinically significant changes in laboratory values will be reported as AEs.

Hematology with differential, serum chemistry, lipid profile, and urinalysis samples will be collected at the specific times starting at screening and throughout the study according to the schedule of events (Table 1).

In addition: all female subjects of childbearing potential will have a serum pregnancy test at Screening, all other site visits except for Visit 3 which is by phone, and Visit 6/Early Termination Visits. Urine pregnancy tests will be done only at Screening. Any positive urine pregnancy test will be confirmed with a serum pregnancy test. Results must be available prior to protocol mandated study treatment. Subjects with positive results at the Screening or Baseline Visits will be ineligible for study entry. Any female subject that becomes pregnant during the study will be immediately withdrawn and will have the pregnancy reported as per Section 9.4.

If applicable, the subject's agreement to use contraception throughout their study participation, and for 28 days after ending study participation, will be documented.

HBsAg and HBcAb will be performed at the Screening Visit. Results of these tests must be negative or nonreactive for subjects to qualify for the study.

HCV antibody testing will be performed at the Screening Visit. Results of this test must be negative for subjects to qualify for the study.

IGRA testing for tuberculosis will be performed at the Screening Visit. Results of this test must be negative for subjects to qualify for the study.

Thyroid stimulating hormone (TSH) will be measured at the Screening Visit. Results of this test must be within the normal range for subjects to qualify for the study.

Hemoglobin A1c (HbA1c) testing will be performed at the Screening Visit. HbA1c must be $\leq 6.5\%$ for subjects to qualify for the study. Additional HbA1c tests will be done at specified times during the protocol.

Out-of-Range Laboratory Values

Laboratory values from samples collected at the Screening Visit will be evaluated by the investigator for eligibility of the subject in the study. Clinical laboratory tests may be repeated once to determine subject eligibility.

Laboratory values that fall outside the reference range from samples collected at the Baseline Visit and throughout the study will be assessed by the investigator for clinical significance. If the out of range value is deemed clinically significant by the investigator, an AE will be recorded.

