Study procedures	Visit 1 Screening Day -28 to-1	Visit 2 Baseline Day 1	Visit 3 Phone Day 15 ±1	Visit 4 In Clinic Day 29 ±2	Visit 5 In Clinic Day 43 ±2	Visit 6 In Clinic Day 85 ±3	Visit 7 In Clinic / End of Acthar Taper Day 113 ±3	Early Termination
Superior, central and total corneal staining score (fluorescein)	X	X		X	X	X		X
Nasal, temporal and total conjunctival staining score (lissamine green)	X	X		X	X	X		X
Schirmer's Test	X	X		X	X	X		X
IOP	X					X	X	X
Undilated Fundoscopy	X					X	X	X
Inclusion/Exclusion criteria review	X	X						
Height ^a and weight	X	X				X	X	X
Vital signs ^b	X	X		X	X	X	X	X
Physical examination	X					X		X
Laboratory testing								
Chemistry and others ^c	X	X		X	X	X		X
HbA1c	X	X		X	X	X		X
Serum Pregnancy	X	X		X	X	X		X

Study procedures	Visit 1 Screening Day -28 to-1	Visit 2 Baseline Day 1	Visit 3 Phone Day 15 ±1	Visit 4 In Clinic Day 29 ±2	Visit 5 In Clinic Day 43 ±2	Visit 6 In Clinic Day 85 ±3	Visit 7 In Clinic / End of Acthar Taper Day 113 ±3	Early Termination
Hepatitis Serology ^d	X							
IGRA for TB	X							
Immunological protein assay ^e	X	X				X		X
IXRS contact	X	X		X	X			X
Study Therapy								
Study drug and injection record training		X						
Dispense study drug		X		X	X			
Administer first dose in clinic ^f		X						
Adverse event assessment	X	X	X	X	X	X	X	X
Injection record review				X	X	X	X	X
Concomitant treatment review		X	X	X	X	X	X	X
Start Acthar Taper						X		
End Acthar Taper							X	
Study exit							X	X

AE = adverse events; ET = early termination; HbA1c = glycosylated hemoglobin; IDEEL = Impact of Dry Eye on Everyday Life; IGRA = Interferon gamma release assay; IOP = Intraocular Pressure; ODS = Ocular Discomfort Score; TB = tuberculosis; VAS = Visual Analogue Scale.

^a Height at screening only. Weight at screening, Visits 2, 6, and ET.

^b Blood pressure, respiratory rate, pulse rate and body temperature. For blood pressure, an average of 2 readings after the subject has been seated for \geq 5 minutes at the Screening and Baseline Visits. Single readings after subject has been seated for \geq 5 minutes at all other time points.

^c Refer to Section 9.2.

^d HBsAg, HBcAb, and HCV.

^e Refer to Table 2.

^f The first dose will be administered at the clinic and the subject should be observed for at least 1 hour after dosing.

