4.1. Inclusion Criteria

To be eligible to participate in the study, at the Screening Visit and the Baseline Visit (except as noted below) each subject must:

1. Be adequately informed and understand the nature and risks of the study and must be able to provide a signature and date on the ICF;
2. Be 18 years of age or older at the Screening Visit and may be male or female;
3. Have normal lid anatomy;
4. Have a reported history of severe keratitis in one or both eyes and a history of previous treatment for keratitis within the previous 6 months;
5. Did not respond adequately or did not tolerate previous treatment with topical cyclosporine or LFA-1 antagonist;
6. Have all the following in at least one eye (the same eye) at screening and baseline:
 - a. Have an inferior corneal fluorescein staining score of at least 2 points in any field (Ora Calibra™ Scale) in at least one eye at the Screening and Baseline visits;
 - b. Have a sum corneal fluorescein staining score ≥ 4 , based on the sum of the central, superior, and inferior regions of the cornea (Ora Calibra™ Scale) in at least one eye at the Screening and Baseline Visits;
 - c. Have a sum lissamine green conjunctival score of ≥ 2 , based on the sum of the temporal and nasal regions of the conjunctiva (Ora Calibra™ Scale) in at least one eye at Screening and Baseline visits;
 - d. Have a conjunctival redness score ≥ 1 (0-4 point Ora scale) in at least one eye at the Screening and Baseline Visits;
 - e. Have a Schirmer score ≥ 1 mm and ≤ 10 mm/5min in at least one eye at the Screening and Baseline Visits;
 - f. Have an Ocular Discomfort Score (ODS) of ≥ 2 (0-4 point Ora scale) in at least one eye at the Screening and Baseline Visits;
7. If female, of nonchildbearing potential (history of hysterectomy, bilateral oophorectomy, bilateral tubal ligation; or postmenopausal with no history of menstrual flow in the 12 months prior to the Screening Visit); or, if of childbearing potential, be nonpregnant, nonlactating, and agree to use 2 forms of effective contraception when with a male partner for the duration of the study (through Visit 6). Acceptable forms of contraception include hormonal measures (oral contraceptive pills, contraceptive patch, contraceptive ring, injections), intrauterine devices, double barrier method (condom plus diaphragm, condom or diaphragm plus spermicidal gel or foam, surgical sterilization of the male partner), and abstinence;

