8. If male with reproductive potential, agree to use 2 forms of effective contraception (abstinence, surgical sterilization [vasectomy], or condom with spermicide) with a female partner for the duration of the study (through Visit 6);
9. Subjects must have a mean systolic blood pressure \leq 150 mm Hg and a diastolic blood pressure of \leq 90 mm Hg determined by the average of 2 seated readings taken at least 5 minutes apart at the Screening and Baseline Visits;
10. Be able to communicate effectively with study personnel;
11. Be able and willing to follow all protocol requirements and study restrictions;
12. Be able and willing to return for all study visits

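### Required contraception ends at Visit 6, when the taper starts, and Table 1 has no pregnancy test at Visit 7; Section 7.2.5 asks for both to go further

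*Combined protocol and SAP*

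**What the plan says.** **Contraception.** Inclusion criterion 7 requires women of childbearing potential to "agree to use 2 forms of effective contraception when with a male partner for the duration of the study (through Visit 6"). Criterion 8 puts the same limit on men with reproductive potential: "with a female partner for the duration of the study (through Visit 6"). Section 7.2.5 says that the site will document the subject's "agreement to use contraception throughout their study participation, and for 28 days after ending study participation".

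**Testing.** For women of childbearing potential, Section 7.2.5 requires a "serum pregnancy test at Screening, all other site visits except for Visit 3 which is by phone, and Visit 6/Early Termination Visits". It adds: "Urine pregnancy tests will be done only at Screening". In Table 1 the row "Serum Pregnancy" is marked at Visits 1, 2, 4, 5, 6 and Early Termination. It is blank at Visit 3 (phone) and at Visit 7.

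**Timing.** Table 1 places "Start Acthar Taper" at Visit 6 (Day 85 ±3), and the end of the taper and study exit at Visit 7 (in clinic, Day 113 ±3). Section 3.6 defines completion by the Visit 7 assessments, and Section 5.6.2 treats the study period for prohibited therapies as Baseline through Visit 7. Sections 3.1, 3.2 and 5.1 add an in-clinic safety visit four weeks after the last dose, which has no column in Table 1.

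**Reporting.** Section 7.2.5 states: "Any female subject that becomes pregnant during the study will be immediately withdrawn and will have the pregnancy reported as per Section 9.4". Section 9.3.4 requires all pregnancies to be reported.

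**The concern.** Criteria 7 and 8 equate the duration of the study with Visit 6, but the study does not end there and dosing continues for four more weeks. The entry criteria are what a subject agrees to on joining, and they lapse just as the taper begins.

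On testing, if sites follow Table 1, a subject who stops early has a closing pregnancy test at the Early Termination visit. A subject who completes the taper does not: her last test is at Day 85, before the first taper dose. A pregnancy that begins during the taper could pass unrecognised through study exit. The duty to withdraw and report would still apply, but meeting it would depend on the subject volunteering the information or on an unscheduled test, which Section 7.2 allows as needed.

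The contraception wording is the preventive part. A Visit 7 test only detects exposure that has already happened.

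**Working it through.** The plan gives no figure on this point to reproduce. The check sets the clauses side by side and counts days and doses on nominal visit days.

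| Item | Section 4.1 or Table 1 | Section 7.2.5 |
|---|---|---|
| Contraception ends | Visit 6, Day 85 | End of participation + 28 days |
| Scheduled serum tests, besides Early Termination | Visits 1, 2, 4, 5, 6 | Plain reading: Visits 1, 2, 4, 5, 6, 7 |

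**Doses (Section 5.1)**
- Main phase: 12 weeks × 2 = 24 doses; 24 × 80 U = 1920 U.
- Taper: (2 weeks × 2) + (2 weeks × 1) = 6 doses; 6 × 40 U = 240 U.
- Taper share: 6/30 = 20% of doses; 240/2160 = 11.1% of units.

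**Contraception shortfall if participation ends at Visit 7 (Section 3.6)**
- Section 7.2.5 end date: 113 + 28 = Day 141.
- Shortfall: 141 − 85 = 56 days, of which the first 28 are the taper.
- With visit windows: (110 + 28) − 88 = 50 days to (116 + 28) − 82 = 62 days.

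**Contraception shortfall if participation runs to the later safety visit (Section 3.2)**
- Last dose in taper week 4: Day 106 to 112.
- Safety visit: + 28 = Day 134 to 140.
- Section 7.2.5 end date: + 28 = Day 162 to 168.
- Shortfall: 162 − 85 = 77 days to 168 − 85 = 83 days. A last dose on Day 113 itself would make it 84.

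**Time from last test to exit, only if Table 1 governs**
- 113 − 85 = 28 days; with windows, 110 − 88 = 22 to 116 − 82 = 34 days.

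**Comparison with the longest interval the schedule already accepts during dosing (Visit 5 to Visit 6)**
- 85 − 43 = 42 days; with windows, 82 − 45 = 37 to 88 − 41 = 47 days.
- 6 weeks × 2 = 12 doses; 12 × 80 U = 960 U.
- The taper carries 240/960 = 25% of those units over a shorter interval. What distinguishes it is that Table 1 has no test to close it.

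**Reading the testing sentence.** The only visit it plainly excepts is Visit 3, because it is by phone; Visit 7 is in clinic. If Visit 6/Early Termination is a listed test point, the phrase covering all other site visits still takes in Visit 7. If it is part of the exception, Visit 7 is still not excepted, and the sentence would then contradict the Table 1 marks at Visit 6 and Early Termination.

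**The case against.** **Section 7.2.5 already covers contraception.** It documents agreement for participation plus 28 days, and criterion 11 requires willingness to follow the whole protocol. On this view the 56 days is a distance between two clauses, one of which protects the subject. That is fair as to the protocol read as a whole. It does not remove the conflict: the criteria state a different end date, and a site cannot apply both.

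**Visit 6 was meant as the closing test.** Section 7.2.5 names Visit 6/Early Termination at the end of its list, as Table 1 does, and naming Visit 6 would be redundant if every site visit were already included. This reading is possible, and it makes the testing point less certain than the contraception point. The text does not say so, however, and the sentence would still need rewording.

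**The testing gap is small.** The schedule tolerates a longer interval with four times the units between Visits 5 and 6, and Visit 7 includes adverse event and concomitant treatment review, so staff do see the subject. This stands as a limit on size: the 20% of doses after the last test does not measure excess risk. The remaining weakness is the lack of a closing test for completers.

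**The consequence is not quantified.** The documents do not give the number of subjects affected, and Section 1.3 states no fetal risk. That stands. Even so, the protocol treats pregnancy as serious enough to require two forms of contraception, withdrawal and reporting.

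**The end of participation is itself unclear.** Section 3.2 counts the later safety visit and Section 3.6 does not. That ambiguity is already in the protocol; it affects the length of the shortfall, not its existence.

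**Conclusion.** The concern holds and should be fixed. Criteria 7 and 8 are wrong as written: they end contraception at Day 85 with six 40 U doses still to come. That is 56 days short of Section 7.2.5 if participation ends at Visit 7, or 77 to 83 days if it runs to the safety visit, assuming the last dose falls on Day 106 to 112. This part does not depend on how the testing sentence is read.

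Table 1 also departs from the plain reading of Section 7.2.5 by leaving Visit 7 without a pregnancy test. If Table 1 governs, completers go 28 days and six doses from their last test to exit. The argument does not rest on the term active treatment period in Section 9.4, because Section 3.2 lists the taper separately from active treatment.

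This is a matter of subject safety and internal consistency. It applies to an unstated number of women of childbearing potential and men with reproductive potential among up to 36 subjects, and it changes no efficacy analysis.

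**What to change.** 1. In inclusion criteria 7 and 8, replace the Visit 6 limit with: *throughout study participation and for 28 days after it ends*.
2. In Table 1, mark a pregnancy test at Visit 7. It can be serum, as in Section 7.2.5, or urine with serum confirmation, since Table 1 schedules no other laboratory test at that visit. If urine is chosen, amend the Section 7.2.5 statement that limits urine tests to Screening so that it also names Visit 7.
3. Reword the serum testing sentence in Section 7.2.5 to: *all in-clinic visits through Visit 7/Early Termination*.
4. Leave the Screening urine test and the Baseline serum test as they are.

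The cost is a short amendment: two phrases in the criteria, one table cell, and one sentence in Section 7.2.5 (two if urine is chosen). Women of childbearing potential have one more test at an existing visit, which would be the only blood draw there if serum is used. Women and men have a longer stated contraception period. No visit is added and no analysis changes.

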7.3. Adverse Events

Adverse events will be recorded from signing of the ICF and followed by the investigator until the AE is resolved, resolved with sequela, or stabilized. All safety measures (which includes standard of care activities) should be provided by the study site to the subject. Any study site follow-up should be documented.

Refer to Section [9.3.4](#) for additional details on the handling of AEs and SAEs.

7.4. Treatment Overdose

For this study, any dose of Acthar greater than 80 U within a 24 (± 1) hour time period will be considered an overdose. The sponsor does not recommend specific treatment for an overdose.

In the event of an overdose, the investigator or designee should:

- Contact the MM immediately.
- Closely monitor the subject for any AE/SAE and laboratory abnormalities until the treatment can no longer be detected (at least 48 hours).
- Document the quantity of the excess dose, as well as the duration of the overdose.

7.5. Pharmacokinetic Assessments

Not applicable for this study.

7.6. Genetics

Not applicable for this study.

7.7. Biomarkers

Not applicable for this study.

7.8. Health Economics and Outcomes Research Assessments

Not applicable for this study.

8. STATISTICAL CONSIDERATIONS

8.1. Sample Size Determination

Approximately 36 subjects will be screened in order to have 30 analysable subjects enrolled in this study. No formal sample size calculations will be performed. The sample size was determined empirically.

8.2. Populations for Analysis

For the purposes of analysis, the following populations are defined

- The Modified Intent-to-Treat (mITT) population will include all subjects who receive at least 1 dose of study drug and who contribute any postbaseline efficacy data to the study.
- The Per-Protocol (PP) population will include a subset of the mITT population with subjects who do not have any major protocol deviations.
- The Safety Population will include all subjects who receive 1 or more doses of study drug.

8.3. Statistical Analyses

This section provides a general summary of the statistical methods to be used in analyzing study data. A more detailed statistical analysis plan will be provided in a separate document that will be finalized prior to database lock.

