2.3. Outcome Measures

The primary outcome measure is the proportion of responders who improved on the IDEEL score. There are no secondary outcome measures.

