5.4. Measures to Minimize Bias

This is an open label study, no randomization or stratification will be employed in treatment assignment.

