7.1.2. Patient-reported Outcomes (PROs)

The following 4 questionnaires were used to assess quality of life (QOL) measures ([Sheppard, 2014](#)):

Impact of Dry Eye on Everyday Life (IDEEL) Questionnaire: The IDEEL comprises 57 questions and 3 modules: the impact on daily life module (activity/work limitations and emotional impact), the treatment satisfaction module, and the symptom bother module. Each module is scored from 0 to 100; higher scores on the impact on daily life and treatment satisfaction modules indicate a better quality of life (QOL) and higher treatment satisfaction. In contrast, higher scores on the symptom bother module indicate more bothersome dry eye symptoms. A 12-point difference in symptom bother module scores indicates a clinically important change in bothersome dry eye symptoms ([Grubbs, 2014](#)).

Ocular Discomfort Score (ODS): The ODS is a scale in which subjects are asked to subjectively rate 5 areas of ocular discomfort: ocular discomfort, dryness, grittiness, burning, and stinging. Subjects are asked to grade their discomfort on a 5-point scale where 0 is no discomfort and 4 is constant discomfort ([Stonecipher, 2016](#)).

Visual Analog Scale (VAS) of Eye Dryness: The VAS is a 7-item, patient-reported symptom index with items of eye dryness, burning/stinging, itching, foreign body sensation, eye discomfort, photophobia, and pain. Subjects are asked to subjectively rate each ocular symptom by placing a vertical mark on the horizontal line from 0 to 100 (0 = no discomfort, 100 = maximal discomfort) to indicated their level of discomfort ([Holland, 2017](#)).

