8.3.1. Efficacy Analyses

All efficacy analyses will be performed on the mITT population. Selected analyses may be performed on the Per-Protocol population.

Baseline and change from baseline at each posttreatment visit will be summarized for all numerical variables with descriptive statistics. Frequency and percentage will be calculated for categorical variables. The nominal p-values along with the 95% confidence intervals (CI) will be provided as appropriate. For subjects who have both eyes affected, the change from baseline will be determined based on the eye with the worst severity at baseline. If both eyes have the same severity at baseline, the right eye will be used to determine change from baseline.

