8.3.3. Interim Analyses

No formal interim analyses are planned for this study.

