8.3.4. Handling Missing Data

A full description of the missing data imputation method for all endpoints will be described in the statistical analysis plan.

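### Section 8.3 lets the SAP be finalized at any time before database lock in an open-label, single-arm study, so the undefined IDEEL responder and missing-data rules could be settled after post-baseline results are accessible

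*Combined protocol and SAP*

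**What the plan says.** On timing, protocol section 8.3 states: "A more detailed statistical analysis plan will be provided in a separate document that will be finalized prior to database lock". No earlier event, such as first enrolment or the first post-baseline assessment, is named.

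On design, section 5.4 states: "This is an open label study, no randomization or stratification will be employed in treatment assignment". Section 3.1 describes one treatment regimen for all subjects. Section 9.1.5 provides for no monitoring committee. Section 9.1.7 has the sponsor's medical monitor review the data for safety. No section says who may see efficacy data before the SAP is final. Section 8.3.3 adds: "No formal interim analyses are planned for this study".

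On the outcome, section 2.3 states: "The primary outcome measure is the proportion of responders who improved on the IDEEL score. There are no secondary outcome measures". Section 7.1.2 says "The IDEEL comprises 57 questions and 3 modules", each scored 0 to 100, with symptom bother running in the opposite direction to the other two. It defines no total score. It also says "A 12-point difference in symptom bother module scores indicates a clinically important change in bothersome dry eye symptoms", but does not make this the responder cut-off. Table 1 schedules IDEEL at baseline, at Visits 3, 4, 5 and 6, and at early termination.

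On missing data, section 8.3.4 states: "A full description of the missing data imputation method for all endpoints will be described in the statistical analysis plan".

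Some things are fixed. Section 8.3.1 states: "All efficacy analyses will be performed on the mITT population". It also provides for frequencies and percentages, and for nominal p-values with 95% confidence intervals where appropriate.

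**The concern.** Finalizing an SAP before lock is normal, and it protects a blinded randomized trial because nobody can link outcomes to treatment until the blind is broken. That protection is absent here. With one open-label arm, a subject's change from baseline on IDEEL is itself the efficacy result, visible to anyone with access to the data well before lock.

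This matters because the open choices drive the only outcome measure: which module counts, how large an improvement makes a responder, at which visit, and how a missing score is handled. If they are made with results in view, the reported rate can be the most favourable of several, and its nominal p-value and confidence interval would not reflect the selection. With no control arm, prespecification is the main safeguard left.

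**Working it through.** The protocol gives no alpha, effect size, SD or reference rate, so there is no figure of its own to reproduce. The calculation below illustrates how far the open choices can move the result when the drug does nothing.

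**Inputs from the protocol:** 30 analysable subjects (8.1); 3 modules on a 0–100 scale and a 12-point difference for symptom bother (7.1.2); 4 scheduled post-baseline IDEEL visits (Table 1).

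**Assumptions:** module SD 20; test-retest reliability r = 0.8 (range 0.7–0.9); normal errors, with between-module error correlation 0.5; each module's baseline error shared by its four change scores; no true change.

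**One pre-fixed rule.** Error SD = 20 × √(1 − r). Change SD = 20 × √(2(1 − r)). Responder rate at 12 points = 1 − Φ(12 / change SD).
- r = 0.8: change SD 12.65; 1 − Φ(0.949) = 17%.
- r = 0.7: change SD 15.49; 1 − Φ(0.775) = 22%.
- r = 0.9: change SD 8.94; 1 − Φ(1.342) = 9%.
- Any improvement above zero: 50% whatever the SD.

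**Best of several rules** (simulated trials of 30 subjects, averaging the highest responder rate in each):

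| Rule | Fixed in advance | Best available after the fact |
|---|---|---|
| 12 points, symptom bother, 4 visits | 17% (9–22%) | about 23% (14–28%) |
| 12 points, 3 modules × 4 visits | 17% (9–22%) | about 28% (17–33%) |
| Any improvement, 3 modules × 4 visits | 50% | about 63% |

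Letting the cut-off vary among 12 points, 8 points and any improvement also gives 63%. Every subject who gains 8 or 12 points has also improved, so the any-improvement rule always gives the highest rate. Like for like, selection adds about 6 points (23 − 17), 11 points (28 − 17) and 13 points (63 − 50). The rest of the distance from 17% to 63% comes from the looser cut-off (50 − 17 = 33 points).

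**Nominal tests of mean change.** Over the 12 module-by-visit comparisons, about 18% of null trials show at least one significant improvement at two-sided 0.05. One pre-fixed comparison would give 2.5% in that direction. Counting worsening as well, the figure is about 36%, but only the improvement direction matters here.

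**Sensitivity to the model.** Taking the SD of change directly as 15, 20 or 25, with between-module correlation 0.3–0.7 and between-visit correlation 0.5–0.8 (all assumed), the fixed 12-point rule gives 21%, 27% or 32%. The best of 12 gives 31–44%. Levels shift, but the pattern is the same.

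**Missing data.** Suppose, as an assumption, that 36 subjects are treated, 6 have no value at the chosen visit, and 15 of the other 30 respond. The rate is 15/30 = 50% on observed cases, 15/36 = 42% if missing counts as non-response, and 21/36 = 58% if missing counts as response. This spread remains even when module, cut-off and visit are fixed.

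**The case against.** The strongest reply has four parts.

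*The text sets a latest date only.* An early SAP is allowed, and the SAP is a separate document whose content and date are not known here. That is true. A reader might infer that the SAP will be written just before lock, or that the sponsor will have seen the results by then. The documents support neither: they plan no formal interim analysis, describe review of the data for safety, and ask for case report forms in a timely fashion. What stands is that nothing requires an earlier date or restricts access.

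*Much is already fixed.* A reader might infer that every choice behind the outcome is open. It is not: the instrument, the responder-proportion form, the set of visits, the mITT population and the 95% level are all in the protocol. The worst-eye rule in 8.3.1 cannot alter a questionnaire scored per subject, and the Per-Protocol analyses are optional.

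*The simulated inflation comes from the undefined responder.* This is largely right. If module, cut-off and visit were fixed in the protocol, the best-of-several figures would disappear whatever the SAP date, and mainly the missing-data rule would remain. The two issues should be read together. They are still distinct, because defining the responder in an SAP signed with data in view would not cure the problem.

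*The study is exploratory.* It is a Phase 4 study with no formal sample size and nominal p-values, and it makes no confirmatory claim. That lowers the severity. It does not remove the point, because the protocol names a primary outcome and provides for intervals.

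**Conclusion.** The concern holds in a limited form. The timing rule in 8.3 permits the responder's module, cut-off and visit, and the missing-data rule, to be chosen after post-baseline IDEEL results could have been accessed. It does not show that this will occur.

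Under the stated assumptions, selection among modules and visits raises a null 12-point responder rate from about 17% to about 28%, or to about 23% if only symptom bother is eligible. It raises a null any-improvement rate from 50% to about 63%. A reader might set 63% against 17% and attribute the whole gap to SAP timing; most of that gap is the change of cut-off. The SDs, reliabilities and correlations are assumed, since the protocol gives none.

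Severity: should-fix, read together with the undefined responder.

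**What to change.** In section 8.3, replace the database-lock condition with: *finalized and signed before the first subject's Visit 3 (first post-baseline IDEEL)*. State that the responder module, cut-off, visit and missing-data rule are fixed by that date, and that any later change is dated, justified and labelled post hoc in the report.

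If enrolment has already started, sign the SAP now and state how many subjects had post-baseline IDEEL data at signature.

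The downside is that the SAP, which has to be written in any case, must be written earlier. The change adds no subjects, visits or procedures.
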